12.4 Statistical Methods

12.4.1 Primary Analysis and Associated Planned Analyses

The primary analysis will be performed on the ITT subject population, which consists of all randomized and treated subjects. The change from baseline to Week 48 in the LogMAR acuity will be the primary response. The ETDRS score will not be directly used because there is a clear relationship between the mean and variance and according to Taylor's power law ($\log SD^2 = 1.743 \log mean + 0.48$, $R^2 = 0.839$) the best transformation is the logarithm (slope close to 2 and ease of interpretation of the difference in means of log). Because LogMAR is a logarithmic scale and is well known by ophthalmologists, this scale is retained as the primary one. The change from baseline of the treated eye will be compared to the change from baseline of the sham eye using a mixed model including the subject, the treatment and the baseline as covariates.

The center will not be included in the analysis as the number of subjects recruited per site will be very small. The difference in the mean change from baseline to Week 48 between the two treatment groups and associated 95% confidence interval will be reported. Alternative non parametric analysis (signed Wilcoxon test) will be performed as a sensitivity analysis to decrease the influence of possible outliers.

The treatment effect reflects well the effect on the better- and worse-seeing eye if no marked interaction between the eye status (better- versus worse-seeing) and treatment exists. To verify this hypothesis, a model including the subject as a random factor, the treatment as a fixed factor as well as the eye status (better- or worse-seeing) and the interaction between eye status and treatment will be fitted. If the P-value of the interaction test is below 0.15 a potential interaction is detected. In that case the better-seeing eye treated with GS010 will be compared to the better-seeing eye treated with sham and the worse-seeing eye treated with GS010 will be compared the worse-seeing eye treated with sham in an ANCOVA model including the LogMAR at baseline and the treatment. The study is then powered $(1-\beta=0.8)$ to detect a difference of approximately 30 letters between the two treatments.

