A meta-analysis combining study GS-LHON-CLIN-03A (RESCUE) and study GS-LHON-CLIN-03B (REVERSE) is planned to verify whether the treatment effect at Week 48 as well as at Week 96 is dependent upon the time from onset of disease. If the treatment effect does not depend upon the eye status, a model using the change from baseline as the response, the subject as a random factor, the treatment as a fixed factor, the time from the onset of disease as a covariate and the interaction between the treatment and the time from the onset will be fitted. If the treatment effect is not the same in the better-and worse-seeing eye, a model will be fitted for the better-seeing eye and another model will be fitted for the worse-seeing eye. The subject factor will not be included in the model, but the LogMAR at baseline, the treatment, and the time from onset of disease will be included.

The generalizability of the treatment effect across countries will be addressed in the metaanalysis because the number of subjects per country could be sufficient to detect major heterogeneity.

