12.4.2 Secondary Analysis

The treatment estimate at Week 96 will be based on the same statistical approach as the primary endpoint analysis. Another analysis will compare time course of the response up to Week 96 using the mixed model procedure. The responder analyses at both Week 48 and Week 96 will be based on a McNemar test for paired samples. To verify whether the treatment effect is dependent upon the better-seeing eye or the worse-seeing eye at study entry, a test of homogeneity of subgroups (better-seeing or worse-seeing eye treated) effects in stratified paired binary data (Zhao 2014) will be performed.

Like the primary endpoint, a meta-analysis will be performed combining both studies (GS-LHON-CLIN-03A (RESCUE) and study GS-LHON-CLIN-03B (REVERSE). A conditional logistic model will be used to assess the effect of better- and worse-seeing eye at study entry and the effect of time from onset of disease and the effect of treatment.

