## 3.3 SAMPLE SIZE CONSIDERATIONS

Sample size calculation is based on the primary endpoint (LogMAR) and on the paired comparison of treated and sham eye. There is no published data regarding the within subject variance and the sample size calculation through paired comparison will therefore be very speculative for two reasons. The first reason is the within subject correlation between right and left eye and the second reason is the absence of information on the within and between subject variance of the LogMAR. Usually the within subject correlation is positive and the use of a null correlation is conservative. The absence of information on the LogMAR requires a second rough

approximation of the mean and variance of LogMAR because the mean of ETDRS (Lam et al. 2014) is highly correlated to the variance of ETDRS ( $R^2 = 0.839$  for the log-log relationship). This correlation is in favor of the use of the LogMAR to stabilize the variance but the transformation from ETDRS mean and variance to LogMAR mean and variance requires additional assumptions. Starting with a mean 23.4 and a standard deviation of 28.3 (Lam et al. 2014) and a difference of 20 letters on average between treated and sham eye, using the relationship between the log mean and the log variance obtained with Lam et al. (2014) results (log variance =  $1.743 \log \text{mean} + 0.48$ ,  $R^2 = 0.839$ ) and assuming a perfect lognormal distribution of ETDRS, the difference in means of the lognormal distributions is 0.65 (3.32 - 2.67) and the pooled standard deviation of the log distributions is 0.914. Assuming no correlation between both eyes, the within subject standard deviation is  $(2 \times 0.914^2)^{0.5} = 1.29$ . The standardized difference in means is therefore  $0.65/1.29 = 0.504$  rounded to 0.50. The sample size required to get a power of 85% is exactly 36 subjects.

In GS-LHON-CLIN-01(Phase I/II study), at Week 48 the standard deviation (SD) for visual acuity of the between-eye difference in change from baseline was calculated as 0.594. Considering that in Phase III studies of GS010 detection of a 15 ETDRS letters or 0.3 LogMAR difference between treated and untreated eyes at outcome is a clinically reliable difference, the SD of the difference of 0.594 would provide a power/probability of 84% to detect such a difference based on the enrolment goal of 36 subjects each in the RESCUE and REVERSE Phase III clinical trials.

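### In the pooled RESCUE and REVERSE analysis, the separate better-eye and worse-eye models omit the treatment-by-time-from-onset interaction, so as written they cannot answer the question the pooling is meant to settle

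*Protocol*

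**What the plan says.** Protocol 12.4.1 gives the purpose of pooling the two studies: to verify "whether the treatment effect at Week 48 as well as at Week 96 is dependent upon the time from onset of disease". It then sets out two branches.

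- **Effect does not depend on eye status.** One model for the change from baseline, with subject as a random factor, treatment, time from onset, and a further term: "the interaction between the treatment and the time from the onset will be fitted".
- **Effect differs between better- and worse-seeing eyes.** Here "a model will be fitted for the better-seeing eye and another model will be fitted for the worse-seeing eye". Subject is dropped, and "the LogMAR at baseline, the treatment, and the time from onset of disease will be included". Nothing else is listed.

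The readable SAP does not describe the pooled analysis. The nearest items are in SAP 4.3 and the sensitivity lists of SAP 9.5.1, where duration of vision loss enters as a covariate, again with no interaction with treatment.

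**The concern.** Asking whether a treatment effect depends on time from onset is a question of effect modification. Its answer is the coefficient of treatment by time. The first branch has that coefficient and the second does not.

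Protocol 12.1 describes a population affected for 180 days or less and cites evidence that benefit may be greatest early in the disease. In the readable documents, the pooled analysis is the only place where a treatment-by-time interaction is planned, so it is the only direct test of that idea. If the effect turns out to differ by eye status, a programmer following the text would fit main effects only and would report no estimate, interval or p-value for the dependence on time. The better-eye comparison is not a side issue either: SAP 9.5.1 makes best-seeing GS010 eyes against best-seeing sham eyes the primary analysis for the FDA.

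**Working it through.** **Terms side by side**

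| Term | Effect does not depend on eye status | Effect differs by eye status (each model) |
|---|---|---|
| Subject (random) | yes | no |
| Baseline LogMAR | not listed | yes |
| Treatment | yes | yes |
| Time from onset | yes | yes |
| Treatment × time from onset | yes | not listed |

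**What the second model can estimate.** Write it as

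E[change] = a + b·baseline + c·treatment + d·time.

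The treatment effect at any time t is E[change | GS010, t] − E[change | sham, t] = c. Its derivative with respect to t is 0 by construction. The coefficient d describes how outcome varies with time from onset in both treatment groups alike. It says nothing on whether the treatment effect varies. With a term e·treatment·time added, the effect becomes c + e·t, and e answers the question.

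**The plan's own figures.** The protocol states no power or precision for the pooled analysis. The inputs that bear on it are in SAP 3.3: an "enrolment goal of 36 subjects each in the RESCUE and REVERSE Phase III clinical trials", and an SD of 0.594 for the between-eye difference in LogMAR change. The SAP's 84% power for a 0.3 LogMAR difference with 36 subjects reproduces: the standardized difference is 0.3/0.594 = 0.505, and the noncentral t gives 83.8%. Pooling gives 36 + 36 = 72 subjects, so 72 eyes of each status.

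**Simulation check.** The setting is assumed: 72 eyes of one status, 36 GS010 and 36 sham; onset times uniform over 0–6 months in half and 6–12 months in the other half; mean effect −0.30 LogMAR at 6 months; residual SD 0.42; 4,000 replicates. Slopes are given as absolute size.

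| True change in effect per month | Treatment estimate, main effects only | Slope recovered with interaction | Rejection rate of interaction test at 5% |
|---|---|---|---|
| 0 | −0.302 | 0.000 | 5.3% |
| 0.03 | −0.300 | 0.031 | 17.6% |
| 0.05 | −0.300 | 0.050 | 39.5% |
| 0.10 | −0.297 | 0.100 | 91.2% |

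The main-effects model returns about −0.30 whatever the true slope. The model with the interaction recovers it.

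**Precision after the fix.** For onset times spread uniformly over R months, the SD of time is R/√12 and

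SE(e) ≈ 2·SD / (√72 · R/√12).

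With SD = 0.594/√2 = 0.42 (no correlation between eyes) and R = 12, SE = 0.84/(8.485 × 3.464) = 0.0286 LogMAR per month. The slope detectable with 80% power is (1.960 + 0.842) × 0.0286 = 0.08 per month. Normal-approximation power is about 18%, 42% and 94% for slopes of 0.03, 0.05 and 0.10.

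The documents give neither the REVERSE onset window nor the between-eye correlation. An SD of 0.594 per eye would correspond to a correlation of 0.5, since 0.594/√(2 × 0.5) = 0.594. Over R = 9 to 18 months and SD = 0.42 to 0.594, power for 0.05 per month runs from 15% to 75%, and the detectable slope from 0.053 to 0.151.

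Multiplying the detectable slope by R removes the dependence on spread: 2.80 × 2 × SD × √(12/72) = 2.29 × SD. That is about 0.96 LogMAR (SD 0.42) to 1.36 LogMAR (SD 0.594) between the earliest- and latest-treated eyes.

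**The case against.** The best defence is that the second branch only amends the first: subject comes out, baseline LogMAR comes in, and the interaction carries over unstated, because the stated purpose governs both branches. This makes a drafting omission more likely than a deliberate choice. It does not rescue the text, because the sentence lists treatment and time from onset again, both already in the first model, and leaves out only the interaction.

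It is also fair to say that this is a cross-study analysis outside the readable objectives, that SAP 9.5.3 spends all the alpha on the primary endpoint, and that redacted SAP text or a separate meta-analysis plan may specify the model in full. These points limit the weight of the concern.

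Several stronger readings are tempting, and the documents do not support them.

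- **The pooled responder model fails in the same way.** Protocol 12.4.2 also lists no interaction, but it asks only for the effect of eye status, "the effect of time from onset of disease and the effect of treatment". It does not itself ask whether the treatment effect varies with time.
- **Time from onset cancels out of that conditional logistic model.** It does so only if it is a single value per subject. The SAP 5.6 definition of vision loss duration uses an onset date for each eye. An eye-level time does not cancel where the two eyes differ, and its main effect should not be removed.
- **Treatment by eye status should be added there.** With matching on subject, take better-eye minus worse-eye differences in (treatment, eye status, product). They are (1, 1, 1) if the better eye is treated and (−1, 1, 0) if the worse eye is. The product equals (treatment + eye status)/2 in every pair, so it cannot be estimated beside both main effects.
- **The first branch is wrong to leave out baseline LogMAR.** That is a preference for consistency. The eye-status interaction model earlier in 12.4.1 does not list it either.
- **The second branch would be entered about 15% of the time by chance.** That borrows the single-study rule, "If the P-value of the interaction test is below 0.15 a potential interaction is detected". The pooled paragraph gives no threshold and does not refer to that one.

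**Conclusion.** The concern holds for the two eye-status models in Protocol 12.4.1. As written, they fix the treatment effect over time from onset and cannot answer the question for which the studies are pooled. This follows from the listed terms and needs no numerical assumption. It rests on reading the list as complete, and on no unseen document specifying the model differently.

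The consequence is confined to this planned pooled analysis, and within it to the case where the effect differs by eye status. The primary comparison, its alpha and N=36 do not change. The data can support the missing term. The precision figures are illustrations under an assumed onset spread and residual SD, and suggest that only a steep gradient would be detected reliably.

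**What to change.** In Protocol 12.4.1, and in whatever plan governs the pooled analysis, add the treatment-by-time-from-onset interaction to both the better-eye and the worse-eye model. Keep baseline LogMAR and the main effects of treatment and time. Report the interaction estimate with its 95% CI at Week 48 and Week 96 as the answer to the stated question. Given the likely power, a non-significant interaction should not be read as showing that time from onset does not matter.

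The change is one added phrase and needs no new data. It uses one degree of freedom per model: with 72 eyes, the residual degrees of freedom go from 72 − 4 = 68 to 67. It should be made before the randomization code is broken, because Protocol Appendix V bars SAP amendments after that point and treats additions as ad hoc.

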12.4.2 Secondary Analysis

The treatment estimate at Week 96 will be based on the same statistical approach as the primary endpoint analysis. Another analysis will compare time course of the response up to Week 96 using the mixed model procedure. The responder analyses at both Week 48 and Week 96 will be based on a McNemar test for paired samples. To verify whether the treatment effect is dependent upon the better-seeing eye or the worse-seeing eye at study entry, a test of homogeneity of subgroups (better-seeing or worse-seeing eye treated) effects in stratified paired binary data (Zhao 2014) will be performed.

Like the primary endpoint, a meta-analysis will be performed combining both studies (GS-LHON-CLIN-03A (RESCUE) and study GS-LHON-CLIN-03B (REVERSE). A conditional logistic model will be used to assess the effect of better- and worse-seeing eye at study entry and the effect of time from onset of disease and the effect of treatment.

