2.2 Secondary

- To evaluate the efficacy of GS010 compared with sham over the follow-up period and at Week 96 in the change from baseline of the LogMAR.
- To verify whether the efficacy at Week 48 and at Week 96 of GS010 compared with sham and measured by the change from baseline in the LogMAR is dependent upon the treatment of the better- or the worse-seeing eye.
- To verify whether the rate of responders at Week 48 and 96 is dependent upon the treatment received and whether the magnitude of the treatment effect is dependent the treatment of the better- or worse-seeing eye at entry.
- To assess the effect of GS010 on parameters measured with high resolution SD-OCT.
- To assess the effect of GS010 on visual fields obtained with the Humphrey Visual Field (HVF) Analyzer II.
- To assess the effect of GS010 on contrast sensitivity measured with the Pelli-Robson chart.
- To assess the effect of GS010 on color vision measure with the Farnsworth-Munsell 100 Hue color test.

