8.6 Method of Assigning Treatment

The right eye of each subject will be randomly allocated to receive either GS010 or sham treatment in a 1:1 allocation ratio. The fellow (left) eye will receive the treatment not allocated to the right eye. Therefore, each subject will receive GS010 in one eye and sham treatment in the fellow eye. Prior to randomization, each subject's better- and worse-seeing eye will be determined. Efron's minimization method will be used in the randomization process to balance as much as possible the two treatment groups (GS010 and sham) in the better-seeing eyes.

To enroll a subject (Visit 1), the Investigator will call an interactive response system (IRS) and provide brief details about the subject to be enrolled. Each subject will receive a subject number assigned at screening, which will serve as the subject identifier throughout the study. The subject number will be required in all communication between the Investigator (or designee) and the IRS regarding a particular subject. Subject numbers will be tracked via the IRS.

To randomize a subject (Visit 2), the masked Investigator (or designee) will call the IRS and provide brief details about the subject to be randomized. Eligible subjects will be randomized in a 1:1 ratio (right/left eye), taking into account the Efron's minimization method, using the IRS.

The IRS User Guide will describe the steps of the randomization process from the subject's screening up to before IVT injection.

An algorithm with a testing hierarchy will be employed prior to randomization to determine the better- and worse-seeing eye of each subject, as follows:

- 1. ETDRS visual acuity score for subjects able to read the ETDRS chart. The eye with the higher ETDRS score is the better-seeing eye. For subjects who cannot read the ETDRS chart ("off chart" subjects) a standard study procedure will be used to determine visual acuity based on counting fingers at a given distance. The eye with the best visual acuity based on this method is the better-seeing eye. If one eye of a subject is able to read letters on the ETDRS chart and one eye cannot, the eye able to read the ETDRS chart is the better-seeing eye.
- 2. SD-OCT parameters (to be used if there is no inter-eye difference based on Criterion 1):

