12.2 Sample Size

Sample size calculation is based on the primary endpoint (LogMAR) and on the paired comparison of treated and sham eye. There is no published data regarding the within subject variance and the sample size calculation through paired comparison will therefore be very speculative for two reasons. The first reason is the within subject correlation between right and left eye and the second reason is the absence of information on the within and between subject variance of the LogMAR. Usually the within subject correlation is positive and the use of a null correlation is conservative. The absence of information on the LogMAR requires a second rough approximation of the mean and variance of LogMAR because the mean of ETDRS (Lam et al. 2014) is highly correlated to the variance of ETDRS ($R^2 = 0.839$ for the log-log relationship). This correlation is in favor of the use of the LogMAR to stabilize the variance but the transformation from ETDRS mean and variance to LogMAR mean and variance requires additional assumptions. Starting with a mean 23.4 and a standard deviation of 28.3 (Lam et al. 2014) and a difference of 20 letters on average between treated and sham eye, using the relationship between the log mean and the log variance obtained with Lam et al. (2014) results (log variance = 1.743 log mean + 0.48, $R^2 = 0.839$) and assuming a perfect lognormal distribution of ETDRS, the difference in means of the lognormal distributions is 0.65 (3.32 - 2.67) and the pooled standard deviation of the log distributions is 0.914. Assuming no correlation between both eyes, the within subject standard deviation is $(2x0.914^2)^{0.5} = 1.29$. The standardized difference in means is therefore 0.65/1.29 = 0.504 rounded to 0.50. The sample size required to get a power of 85% is exactly 36 subjects.

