**Secondary Objectives:**

- To evaluate the efficacy of GS010 compared with sham over the follow-up period and at Week 96 in the change from baseline of the LogMAR.
- To verify whether the efficacy at Week 48 and at Week 96 of GS010 compared with sham and measured by the change from baseline in the LogMAR is dependent upon the treatment of the better- or worse-seeing-eye.
- To verify whether the rate of responders at Week 48 and 96 is dependent upon the treatment received and whether the magnitude of the treatment effect is dependent upon the treatment of the better- or worse-seeing eye at entry.
- To assess the effect of GS010 on parameters measured with high resolution SD-OCT
- To assess the effect of GS010 on standardized automated visual fields obtained with the Humphrey Visual Field (HVF) Analyzer II.
- To assess the effect of GS010 on contrast sensitivity measured with the Pelli-Robson chart.
- To assess the effect of GS010 on color vision measured with the Farnsworth-Munsell 100 Hue color test.

[REDACTED]

[REDACTED]

[REDACTED]

[REDACTED]

[REDACTED]

[REDACTED]

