### Eye responders

The responder analyses at both Week 48 , Week 72 and Week 96 will be based on a McNemar test comparing all-GS010 eyes against all-Sham eyes.

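### The responder homogeneity test in Protocol 12.4.2 does not isolate the treatment by eye-status interaction: any better/worse responder gap in sham eyes is added to it

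*Protocol*

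**What the plan says.** One secondary objective in Protocol 2.2 is to find out "whether the magnitude of the treatment effect is dependent the treatment of the better- or worse-seeing eye at entry", for the responder rate at Weeks 48 and 96. The SAP's secondary objectives repeat it: "whether the magnitude of the treatment effect is dependent upon the treatment of the better- or worse-seeing eye at entry".

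The method for this objective is in Protocol 12.4.2: "a test of homogeneity of subgroups (better-seeing or worse-seeing eye treated) effects in stratified paired binary data". The layout is fixed by Protocol 8.6, where "each subject will receive GS010 in one eye and sham treatment in the fellow eye". The same section says that "Efron's minimization method will be used in the randomization process to balance as much as possible the two treatment groups" among better-seeing eyes, so the two strata should be of similar size.

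For LogMAR, Protocol 12.4.1 does something different. It fits eye status, treatment and their interaction. If an interaction is suspected, "the better-seeing eye treated with GS010 will be compared to the better-seeing eye treated with sham", and likewise for worse-seeing eyes.

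In the readable SAP 9.5.5, the eye-responder analysis is "based on a McNemar test comparing all-GS010 eyes against all-Sham eyes", and the subject-responder analysis is a randomization test of the overall rate. Neither addresses eye status. Parts of the SAP are redacted.

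**The concern.** Within a subject the GS010 eye and the sham eye always have opposite eye status. A within-subject treatment difference is therefore also a better-versus-worse difference, with one sign in one stratum and the opposite sign in the other. Comparing the strata does not remove that component; it doubles it.

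A gap between better and worse eyes is plausible here. Under Protocol 3.2 an eye counts as a responder if it is better than 20/200, with no gain required. Protocol 8.6 ranks eyes first on visual acuity. Protocol 5.2.1 requires vision loss in at least one eye only, so a fellow eye may be little affected at entry.

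At stake is the answer to a named secondary objective. The test could report that the GS010 effect depends on which eye is treated when only eye status matters, and it could fail to see a dependence that is real.

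**Working it through.** **The plan's own figure.** No power or error rate is stated for the homogeneity test. The only sizing is for the paired primary comparison: "The sample size required to get a power of 85% is exactly 36 subjects". With a standardized difference of 0.50 and two-sided 5%, the normal formula gives ((1.960 + 1.036)/0.50)² = 35.9, so 36 subjects. The stated figure reproduces (power 85.1%; a noncentral-t calculation gives 83.1%).

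**The contrast.** Write GB, SB, GW and SW for the responder probabilities of GS010 better, sham better, GS010 worse and sham worse eyes.

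- Paired effect, better eye treated: GB − SW.
- Paired effect, worse eye treated: GW − SB.
- Difference tested: (GB − SW) − (GW − SB) = (GB + SB) − (GW + SW). This is twice the average better-minus-worse gap.
- Interaction wanted: I = (GB − SB) − (GW − SW).
- Substituting: difference tested = 2(SB − SW) + I.

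The test targets I only when SB = SW. The same algebra holds on the conditional log-odds scale, so a different effect measure does not remove the problem.

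**Three numerical cases (GB/SB/GW/SW, assumed).**

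| Rates | Better eye treated | Worse eye treated | Difference tested | True I |
|---|---|---|---|---|
| 50/50/20/20 | 50 − 20 = +30 | 20 − 50 = −30 | 60 | 0 |
| 60/20/40/40 | 60 − 40 = +20 | 40 − 20 = +20 | 0 | 40 |
| 60/20/20/20 | 60 − 20 = +40 | 20 − 20 = 0 | 40 | 40 |

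**Rejection rates by simulation.** The assumptions are 18 + 18 subjects, latent-normal inter-eye correlation 0 to 0.6, a t-type test of the difference in paired risk differences, and the two-sided 5% level. The last column compares the number of responding eyes per subject (0, 1, 2) between the two groups. Its mean difference is (GB + SW) − (GW + SB) = I.

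| Rates | True I | Planned test | Eyes-per-subject contrast |
|---|---|---|---|
| Better = worse = 20% | 0 | about 5% | about 5% |
| Better 30%, worse 20% | 0 | 16-21% | about 5% |
| Better 40%, worse 20% | 0 | 45-63% | about 5% |
| Better 50%, worse 20% | 0 | 77-92% | about 5% |
| 60/20/40/40 | 40 points | about 5% | 33-42% |
| 60/20/20/20 | 40 points | 50-67% | 40-49% |

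**Sensitivity to the form of the test.** A version based on the odds ratio in discordant pairs (Fisher) rejects less often. With no interaction, correlation 0 to 0.8 and a treatment effect of 0 or 20 points, it gives 25-52% at a 20-point gap, against 42-77% for the risk-difference version over the same range. The protocol states no level for this test. At the 15% level that 12.4.1 uses for LogMAR, the risk-difference version gives 30-48% at a 10-point gap and 63-90% at 20 points.

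**The case against.** **The test does respond to the interaction.** The difference tested contains I. If sham better and worse eyes respond equally, the test targets exactly the right quantity, and in the 60/20/20/20 case it rejects more often than the replacement. This stands. A reader might infer that treatment cancels out, or that the test has no power for a real dependence; neither follows. Power falls to the 5% level when the average gap is zero, and the case that shows it (60/20/40/40) needs sham worse eyes to outperform sham better eyes, the reverse of the expected direction.

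**The gap is unknown.** A reader might infer that the test would usually declare a false dependence. The documents give no responder rates, so this is not supported. A gain of 15 letters, the other route to response, does not automatically favour better eyes. The protocol summary gives a median second-eye delay of 2 months, so fellow eyes may converge by Week 48. At a 10-point gap the false-dependence rate is well under one half.

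**The exact statistic is in a cited paper that was not available here.** This is true, and it is why the percentages are tied to a stated version. The algebra depends only on the strata and the pairing, which the protocol does state.

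**The SAP may already have replaced the test.** Text around the responder analyses is redacted, so one can say only that the readable text shows no replacement, not that none exists.

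**The conditional logistic model in 12.4.2.** A reader might extend the criticism to it. That model is planned for the pooled meta-analysis, with no stated interaction term. Such an interaction is constant within each pair and could not be estimated by that model, but the plan does not say that it will be.

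**It is secondary.** SAP 9.5.3 spends all the alpha on the primary endpoint and treats the rest as supportive. LogMAR dependence on eye status is handled with the right contrasts. This limits the weight of the point but does not repair the test.

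**Conclusion.** The concern holds in limited form. The homogeneity test in Protocol 12.4.2 estimates twice the sham-eye gap plus the interaction, so it is valid for its objective only if sham better and worse eyes respond equally. Whenever that cannot be assumed, a rejection cannot be attributed to the interaction and a non-rejection does not rule one out.

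The algebra needs no assumed rates; the size of the error does. False dependence runs from about 5% with no gap to 77-92% at 50% versus 20%, assuming 18 subjects per stratum, correlation 0 to 0.6 and a risk-difference test at 5%. An odds-ratio version gives lower figures.

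The primary analyses and their conclusions are not affected.

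**What to change.** Replace the homogeneity test in Protocol 12.4.2 and state the replacement in the responder part of SAP 9.5.5:

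- Report responder differences for Best-GS010 versus Best-Sham and for Worst-GS010 versus Worst-Sham, each with a 95% CI, at Weeks 48 and 96.
- Test the interaction on the risk-difference scale by comparing responding eyes per subject (0, 1, 2) between subjects whose better eye was treated and those whose worse eye was treated, by permutation, with the difference in mean count as the statistic.
- A marginal logistic model with treatment, eye status and their interaction, clustered on subject, is an alternative. It measures interaction on the log-odds scale and is not equivalent to the count comparison, so name one in advance.

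The cost is a change of wording and one table, to be made before the randomization code is broken, since Protocol Appendix V bars later SAP amendments. The downside is precision. The contrast is between subjects, with about 33-50% power for a 40-point interaction in the cases simulated. The result should be presented as an estimate with its interval, and a non-significant test should not be read as evidence that the effect is the same in both eyes.
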